In response to RFA-HD-12-195, this treatment project is designed to address two significant public health challenges- the need for validated, manualized treatments for young children with ASD that are cost-efficient and feasible for community-based implementation, and the need to reduce the age of entry into early intervention. The major objective is to directly compare two parent intervention conditions for 9 months: 1) an information, education and support group (Group) offered weekly, and 2) an individualized parent-implemented intervention (Individual) offered in 2 weekly sessions to teach parents how to embed strategies to support social communication skills within everyday routines, activities, and places. The Emory ACE Center will recruit 92 parent-infant dyads at 12 months of age from theboth high and low risk siblings being studied. Inclusion criteria for high risk infants will be a positive screen on 2 of 4screening measures indicating the presence of diagnostic features of ASD by 12 months of age. Inclusion criteria for low risk infants will be a positive screen on 2 of 4 screening measures indicating the presence of diagnostic features of ASD by 12 months of age. Families will be randomly assigned to either Group or Group +Individual for 9 months. Outcome measures of social communication, autism symptoms, developmental level, and adaptive behavior will be gathered every 6 months from 12 to 36 months of age to measure treatment and follow-up effects. Measures of parent transactional support and child active engagement will be collected monthly beginning at 12 months until 36 months of age to examine change in developmental trajectories.

This project is conceptualized as a series of research questions (RQ) for each specific aim to examine the effects of intervention on outcomes of toddlers with ASD. The specific aims and research questions are:

Aim 1. Effectiveness of Treatment: To compare the effects of Group alone to Group plus Individual implemented from 12 to 21 months of age on outcome measures of social communication skills, autism symptoms, developmental levels, and adaptive behavior from 12 to 36 months. Research will address specific questions with regard to whether there are: RQ1a) differences in growth trajectories from 12 to 36 months on social communication skills and autism symptoms, and RQ1b) differences in trajectories of developmental level and adaptive behavior from 12 to 36 months for children receiving

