Sample Recruitment. 92 parent-child dyads will participate in this study. The Emory ACE Center will recruit 92 parent-infant dyads at 12 months of age from the pool of 230 "High-Risk for Developing ASD" younger siblings and from the pool of 100 low risk infants being studied. Inclusion criteria for high-risk infants will be a positive screen on 2 of 4 screening measures indicating the presence of diagnostic features of ASD by 12 months of age. In addition, one of these positive screens must be a SORF measure. Inclusion criteria for low-risk infants will be a positive screen on 3 of 4 screening measures, including positive screens on both SORF measures. It is important to note that a diagnosis of ASD cannot be made reliably at 12 months of age but early signs will be evident in children who will end up with ASD, the broader autism phenotype (BAP), or developmental delay (DD). The Clinical Assessment Core will follow children and clinical diagnosis will be confirmed at 36 months of age.

The following screening protocol will be used with infants at 9 and 12 months of age. The procedures and records for the screening protocol are part of the Clinical Assessment Core and are covered in a separate IRB application. All 230 infants will be given the *Infant-Toddler Checklist* (ITC) a broadband parent report screen for communication that has norms and cut scores at each month from 6 to 24 months of age and has been documented to detect children with ASD down to 9 months of age. Infants who have a positive screen on the ITC will be given the following three autism-specific screening tools: 1) Early Screening for Autism and Communication Disorders (ESAC), an autism-specific parent report screen with 35 recognition format or closed-choice items and 6 open-ended items; 2) Systematic Observation of Red Flags (SORF) Clinic, the SORF rating from the CSBS (see Clinical Assessment Core), Behavior Sample from a video recording of a structured observation in a clinical setting; and 3) SORF-Home, the

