Data Analytic Strategy. The main research aims and hypotheses will be analyzed using a series of mixed models, focusing on Growth Curve Modeling (GCM) and Random-Effects Regression (RER) as more powerful alternatives to repeated measures ANOVA, and estimates of effect sizes will be obtained. We anticipate that effect size estimates will be conservatively derived from simple inspection of observed differences in treatment versus control means divided by the appropriate standardizer (either the control standard deviation or the pooled standard deviation, depending upon whether the treatment is inducing group differences in variances or not). The research aims compare growth trajectories (or residualized change, or outcome only, depending on the dependent variable of interest) for children in the treatment and control groups. It is hypothesized that children receiving the Group plus Individual condition will show significantly faster growth trajectories or change on the MAETS, which will mediate social communication, autism symptoms, developmental level, and adaptive behavior outcomes. Unconditional models that vary in complexity will be used to determine the most parsimonious models for estimating growth in this sample. After fitting the overall model, we will perform fixed-effects contrasts to test for cross-sectional differences between the two groups at points along the curve. Aims 2 and 3 build upon these models to investigate potential mediator and moderator variables that may predict response to treatment. Moderator variables such as initial level of child or parent performance and measures of family functioning will be interacted with treatment group to investigate potential moderating relationships. To investigate potential mediators of treatment effectiveness such as MAETS, we will follow standard strategy for testing mediational effects in a multilevel design where fidelity is conceptualized as a level 1 mediator that can vary by time. Finally, we will consider the possibility that the mediated relation may be stronger in one subgroup than the other (moderated mediation), either because treatment fidelity is accomplished to a greater extent in one subgroup than another or because the link between treatment fidelity and outcome is stronger in one subgroup than another (e.g., treatment fidelity predicts outcome only in individuals with sufficient cognitive abilities). In addition to existing GCM/RER analyses, in synergy with Projects I & II we will repeat our analyses using Functional Data Analysis, a new approach that significantly improves both the detection of common features in trajectory shape as well as the identification of individual spurts or delays relative to the group. Project III will rely on the Data Management and Analysis Core for data storage, management, and transmission to NDAR.

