
Attrition Analyses. All analysis will be done using an intention to treat approach. That is, every subject in the study will be considered in the analysis as a member of the treatment group to which s/he was assigned. We will conduct a series of analyses to examine attrition and its potential effect on the results ⁶⁹, including examining the differential attrition rates for the two treatments and for child and parent characteristics of those completing and those who did not complete one or both treatment conditions, different definitions of dropout, different outcome measures, and treatment-correlated attrition. For the HLM analyses with multiple time points, missing data are not a concern, but differential attrition by treatment group would be. If differential attrition appeared to be a problem, then we would conduct multiple imputation of missing data ⁹⁵ to attempt to estimate the appropriate effect sizes and confidence intervals.

Power Analyses. Power for growth curve modeling was estimated using a power estimation program developed for HLM models 61. When estimating power in growth curve models, there are a number of factors that need to be considered. In addition to alpha level, number of subjects, and anticipated effect size, power can also vary as a function of the number of observations employed and the duration of the study. For these power analyses, we set alpha at .05 and we anticipated as few as 5 and as many as 25 observations per child (per measure). Additionally, we estimated that there would be approximately 10 times as much within person variability than between person variability (the ICC for the person level effect would be .10). Using these estimates, we anticipate that 92 subjects would give us a power=.90 to detect an effect of d=.50 (which corresponds to a medium effect) with five time points estimating linear change. For models testing treatment differences in the presence of quadratic change (with 15 or more assessments per child), power is .95. If attrition drops the sample size to 80 subjects, we will still have power equal to .86 to detect a medium-sized effect (with five assessments estimating linear change) and power=. 91 for those treatment differences tested in the presence of quadratic change. Thus, the minimum power to detect medium effects with 80 subjects is .86. We anticipate that the use of FDA and PACE will increase power.

7. Risks

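### The growth model is chosen by parsimony and the child-level random slope is not protected, so the arm-by-age test can run somewhat above its nominal 5%

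*Combined protocol and SAP*

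**What the plan says.** The first research question under Aim 1 (section 4, Objectives) concerns "differences in growth trajectories from 12 to 36 months on social communication skills and autism symptoms", so the arm-by-age term carries the main result. Section 6, Data Analytic Strategy, sets the model class (growth curve modelling and random-effects regression) and then the selection step: "Unconditional models that vary in complexity will be used to determine the most parsimonious models for estimating growth in this sample". Inference follows from the fitted model: "After fitting the overall model, we will perform fixed-effects contrasts to test for cross-sectional differences between the two groups at points along the curve".

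The plan does not state which random effects are in the candidate set, which criterion decides, what residual covariance is used, or whether robust or small-sample standard errors apply.

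The only variance input is in section 6, Power Analyses, where "the ICC for the person level effect would be .10". No slope variance appears anywhere. Section 5, Sample Recruitment, expects mixed courses among those enrolled: "early signs will be evident in children who will end up with ASD, the broader autism phenotype (BAP), or developmental delay (DD").

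**The concern.** In a linear growth model, the error of the arm-by-age estimate has two parts: the spread of true slopes between children, and visit-level noise. If the random slope is removed because a simpler unconditional fit looks adequate, the first part is no longer carried at child level. Repeated visits of one child then count as nearly independent information on the slope. Intervals become too narrow and p-values too small.

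With 92 children and three to five visits, a modest real slope variance often fails a parsimony test, so this can happen without any analyst error. The tests exposed are the arm-by-age tests for RQ1a and RQ1b and the arm comparison of trajectories on the active-engagement and transactional-support measure (MAETS) in RQ2a. Zero slope variance is hard to defend in a sample expected to split into several developmental courses, studied under a plan that also looks for moderators of response.

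**Working it through.** **Inputs from the documents.** N = 92, alpha .05, five to 25 observations per child, and ICC .10, giving residual variance .90 and child variance .10 on a unit single-visit scale (section 6, Power Analyses). Visit ages:
- 12, 18, 24, 30, 36 months (section 4).
- 12, 24, 36 months, with social communication also at 15 and 21 (section 5, Dependent Variables).
- For MAETS, baseline, monthly for nine months, then quarterly to 36 months, which makes about 15 occasions (section 5, Mediator Variables).

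**Assumptions.** Two-sided test, 1:1 allocation, complete balanced data, normal errors. Let c be the SD across children of true 12-to-36-month change in single-visit SDs, taken as 0.5 to 1.0. The documents do not give c.

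**The plan's own figure.** The stated power of .90 for d = .50 at N = 92 cannot be reproduced uniquely, because the metric of d and the slope variance are missing. Two-sided variants for five visits run from .40 to above .99. The scaling to N = 80 is consistent: (1.960 + 1.282) × √(80/92) − 1.960 = 1.063, which gives .856 (stated .86). This shows only that the planning figures contain no slope variance that could be carried into the check.

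**Step 1: size if the slope is always omitted.** With balanced data the estimated slope difference is the same in both models and only its standard error changes. Let Sxx be the sum of squared age deviations, T the number of visits, and L = (c/24)² × Sxx / .90. Then

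true variance / intercept-only variance = (1 + L) / (1 + L/(T − 1)),

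and the false-positive rate is 2 × [1 − Φ(1.96/√ratio)].

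| Schedule | Sxx | c | L | Ratio | Rate |
|---|---|---|---|---|---|
| Five visits | 360 | 0.5 | .174 | 1.125 | .065 |
| Five visits | 360 | 0.75 | .391 | 1.267 | .082 |
| Five visits | 360 | 1.0 | .694 | 1.444 | .103 |
| Three visits | 288 | 0.5 | .139 | 1.065 | .058 |
| Three visits | 288 | 1.0 | .556 | 1.217 | .076 |
| 15 occasions | 780 | 0.5 | .376 | 1.340 | .090 |

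With c = 0, L = 0, the ratio is 1 and the rate is .05.

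**Step 2: size of the whole select-then-test procedure.** The slope is not always dropped, so the rates in Step 1 are not the rates of the plan. Null trials were simulated in which intercept-only and intercept-plus-slope models were compared in an unconditional maximum-likelihood fit and the arm-by-age term was then tested in the chosen model. Five-visit settings used 20,000 trials each.

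| Five visits, c = 0.5 to 1.0 | Overall false-positive rate |
|---|---|
| LRT (2 df) | .055-.064 |
| AIC | .051-.059 |
| BIC | .064-.078 |
| Slope always omitted | .064-.103 |
| Slope always kept | about .05 |

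At c = 0.75 the slope is dropped in 62% (LRT), 44% (AIC) or 91% (BIC) of trials. Repeat simulations indexed by L gave 5.0-6.3% for LRT or AIC, and a BIC peak of 6.6-7.8% near L = .4-.5 when intercept and slope are uncorrelated at mid-age. The BIC figure falls to about 6.0-6.6% when they are uncorrelated at 12 months.

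At three visits, BIC gives about 6-7%. At 15 occasions, BIC peaks at about 8.5% in one set of runs and 8.8% in another (c = 0.5), and LRT gives about 7.0% at c = 0.5.

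**Step 3: the ends of the range.** With no slope variance there is no inflation. With large slope variance (L = 1, five visits), LRT or AIC drops the slope in only 1-4% of trials and the rate is 5.1-5.2% (BIC 5.3-6.1%). The inflation is therefore confined to modest slope variance.

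**Step 4: cost of always keeping the slope.** The false-positive rate is 4.7-5.1% when slopes vary and about 4.4% when they do not. Where slopes do not vary, power moves from .876 to .871.

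**The case against.** The strongest reply is that model complexity may mean curve shape only. The one distinction of that kind the documents draw is linear versus quadratic change (Power Analyses), and on that reading the plan may already intend what is asked for here. This stands as a possible reading. The text does not say so, however, and no other section fixes the random effects.

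Other text also points away from intercept-only models. Growth curve modelling is preferred to repeated-measures ANOVA, and the analyses are to be repeated with Functional Data Analysis, which looks at individual timing. That shows interest in child-level variation but does not specify the covariance behind the mixed-model test.

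A reader might infer from the single ICC that the analysis will be intercept-only, and so take 6-10% at five visits, or much larger values with correlated monthly residuals, as the expected error rate. The documents do not support that. The ICC is a planning input, no section says the slope will be left out, and the larger values also need a residual correlation that is stated nowhere. Nor do the documents support an unconditional rise to 6-9%, which needs an assumed slope variance together with a BIC-type or intercept-only choice.

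Three further limits stand:
- Adding c = 0.5-1.0 to an ICC of .10 raises the average person-level share to about .13-.20, so the assumption does not sit exactly on the planning value. With ICC .50 and c = 0.5-0.75 the five-visit rates are similar (LRT .057-.060, BIC .069-.076).
- Residualized-change and outcome-only analyses, which the plan allows for some measures, have no random slope to lose. Contrasts at a given age are affected to a degree that depends on the age, and not at all at the mean visit age in balanced data.
- Selection on unconditional fits ignores arm labels, so it does not favour either arm. The fault is only an understated variance.

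**Conclusion.** The concern holds in a limited form. The plan lets a data-driven parsimony rule set the growth model and does not protect the child-level slope, so a real slope variance can be lost before the arm-by-age test. For c = 0.5-1.0, the overall false-positive rate at five visits exceeds 5% by at most about 1.4 points with LRT or AIC and by about 1.5 to 3 points with BIC. The excess is smaller at three visits, which is the schedule section 5 gives for autism symptoms, developmental level and adaptive behaviour. It is largest, about 3.5 to 4 points, with BIC on the 15 MAETS occasions. These sizes rest on an assumed slope variance, an unstated criterion, complete balanced data, normal errors and equal allocation. The direction of the error does not depend on the exact values, provided slopes vary. This is a worthwhile low-cost improvement and does not invalidate the analysis.

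**What to change.** In section 6, Data Analytic Strategy, confine the parsimony search to the shape of the mean curve and name the criterion. State that every arm-by-age test keeps a child-level random intercept and a random coefficient for the growth term being tested, whatever the unconditional fit shows. For measures with three to five visits, an unstructured visit covariance is an acceptable alternative. Use Satterthwaite or Kenward-Roger degrees of freedom. If the model does not converge, keep the fixed part and use standard errors clustered by child; do not delete the slope.

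The change is to wording only and needs no extra data. If slopes truly do not vary, it costs about half a point of power (.876 to .871) and leaves a slightly conservative test (about 4.4%).

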The following dependent variables will be collected by the CAC and coded by raters blind to treatment condition before treatment at 12 months and again at 24 months and 36 months of age. Additionally, the Social Communication Measures will be completed at 15 months and 21 months of age for all children enrolled into the Early Social Interaction project.

Social Communication Measures. The Communication and Symbolic Behavior Scales (CSBS) Behavior Sample will be video recorded to measure social communication. Reliability and validity of the CSBS has been reported (see CAC). The raw scores will be summed to form a social, speech, and symbolic composite.

Autism Symptoms. The Autism Diagnostic Observation Schedule (ADOS) (see CAC) is the gold standard diagnostic measure of ASD. The revised algorithms forming Social-Affect and Restricted Repetitive Behavior ratings of autism symptoms will be used.

Developmental Levels. The Mullen Scales of Early Learning MSEL (see CAC) measures developmental level with separate scores for four cognitive scales that form an early learning composite. A nonverbal DQ based on age equivalent divided by chronological age multiplied by 100 will be calculated from the average of the Fine Motor and Visual Reception scales and a verbal DQ will be calculated from the Receptive and Expressive Language scales.

Adaptive Behavior. The Vineland Adaptive Behavior Scales *VABS-II* (Survey Interview Form; see CAC) yields a standard score in four domains— Communication, Daily Living, Social, and Motor, and an Adaptive Behavior Composite.

Expressive Language Phase. The child's expressive language phase will be determined at each assessment based on the benchmarks delineated by Tager-Flusberg and colleagues and recommended for evaluating the efficacy and comparing outcomes across NIH-funded intervention studies. Based on multiple sources of information about language benchmarks, the language will be categorized as: *Preverbal Communication, First Words, Word Combinations, or Sentences, to* provide a clinically meaningful measure of language outcome.

Mediator Variables

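### The .86 minimum power assumes five assessments per measure, but the protocol schedules ADOS, Mullen and Vineland five times in one section and three in another; under the three-visit schedule .86 is not a minimum for them

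*Combined protocol and SAP*

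**What the plan says.** **Power (section 6, Power Analyses).** Alpha is .05. The paragraph says that power depends on the number of observations, and for the calculation "we anticipated as few as 5 and as many as 25 observations per child (per measure". With 92 children, d=.50 and five time points for linear change, it gives power .90. For 80 children: "we will still have power equal to .86 to detect a medium-sized effect (with five assessments estimating linear change". The companion figures for quadratic change, with 15 or more assessments, are .95 and .91. It concludes: "Thus, the minimum power to detect medium effects with 80 subjects is .86". That sentence names no measure.

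**Schedule in section 4 (Objectives).** One timetable covers all four domains (social communication, autism symptoms, developmental level and adaptive behavior): the measures "will be gathered every 6 months from 12 to 36 months of age to measure treatment and follow-up effects". That is 12, 18, 24, 30 and 36 months.

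**Schedule in section 5 (Dependent Variables).** The dependent variables are collected "before treatment at 12 months and again at 24 months and 36 months of age". One set of measures then gets two extra occasions: "Additionally, the Social Communication Measures will be completed at 15 months and 21 months of age". The ADOS, Mullen and Vineland therefore have three occasions, and the CSBS has five, at 12, 15, 21, 24 and 36 months.

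**Questions to be answered (section 4).** RQ1a asks about "differences in growth trajectories from 12 to 36 months on social communication skills and autism symptoms". RQ1b asks about "differences in trajectories of developmental level and adaptive behavior from 12 to 36 months". RQ2b uses social communication and autism symptom severity at 18, 24 and 36 months.

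Section 5 refers to Appendix 1 for the timeline and to the Clinical Assessment Core for the measures. Neither the appendix nor the Core protocol is in the public text.

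**The concern.** The two schedules cannot both be followed. For the ADOS, Mullen and Vineland they differ by two occasions (18 and 30 months). For the CSBS they agree on the number of occasions but not on the ages. Section 5 gives neither the CSBS nor the ADOS at 18 months, so a site working from that section alone would not collect the 18-month values that RQ2b uses, and these cannot be recovered later.

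The power statement fits only one of the schedules. RQ1a and RQ1b compare trajectories of autism symptoms, developmental level and adaptive behavior, so growth-model power is the power that applies to them. Three occasions lie below the smallest number that the calculation considered. A reader who takes .86 as the lowest power for any of these outcomes would then be relying on a figure that was not calculated for that schedule.

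**Working it through.** **Inputs from the documents.** N=92 with power .90 and N=80 with power .86, both with five assessments and linear change; d=.50; alpha .05; person-level ICC .10.

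**Assumptions, because the documents do not say.** 1:1 allocation; two-sided test; time scaled so that 12 months is 0 and 36 months is 1. Two candidate estimands are tried.

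**Spread of the visits.** SS is the sum of (t − mean t)².

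| Schedule (months) | t | SS |
|---|---|---|
| 12/18/24/30/36 | 0, .25, .5, .75, 1 | .625 |
| 12/24/36 | 0, .5, 1 | .500 |
| 12/15/21/24/36 (CSBS, section 5) | 0, .125, .375, .5, 1 | .606 |

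**Do the stated figures agree with each other?** Solving the noncentral t (N−2 df, noncentrality d_eff·√N/2) gives d_eff=.683 for .90 at N=92 and .688 for .86 at N=80. Carrying .683 to N=80 gives .855, which agrees with .86 to within rounding of the inputs. These effective values are not d=.50, and the text does not give the step that connects them.

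**Illustration A: test of the slope, calibrated to the stated .86.** Let r be the share of the variance of a child's estimated five-visit slope that is true between-child slope variance. The documents do not give r. With another schedule the variance is multiplied by r + (1−r)·(.625/SS). For three visits .625/.500 = 1.25.

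- Noncentrality at five visits, N=80: .688 × √80 / 2 = 3.08.
- r=0: 3.08/√1.25 = 2.75, power .776.
- r=.50: 3.08/√1.125 = 2.90, power .818.
- r approaching 1: power approaches .86.
- CSBS, .625/.606 = 1.031, r=0: 3.08/√1.031 = 3.03, power .850.

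At N=92, calibrated to .90, three visits give .826 at r=0 and .864 at r=.50, approaching .90.

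**Illustration B: group contrast at the end of the fitted line, within-person variance only.** V = .9 × [1/m + (1 − mean t)²/SS], where m is the number of visits. The noncentrality is .50·√N/(2√V).

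| Schedule | V | Power at N=80: normal / t |
|---|---|---|
| Five, equally spaced | .9 × (.200 + .250/.625) = .540 | .861 / .852 |
| Three | .9 × (.333 + .250/.500) = .750 | .733 / .722 |
| CSBS, section 5 | .9 × (.200 + .360/.606) = .714 | .753 / .743 |

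For five visits at N=92 it gives .904 (normal) or .898 (t), so it comes close to both stated linear figures. Calibrated to exactly .86 at N=80, three visits give .73 and the CSBS schedule .75.

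**Which one is the plan's?** This cannot be determined. Illustration B misses the quadratic figure at N=80 (.933 with 15 points, against .91). A one-sided version that adds the random intercept also lands within two points of both linear figures (.912 and .875) and gives .782 at three visits. Several other readings did not reproduce the pair. Going from five visits to three lowered power in every reading tried.

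**The case against.** The strongest reply is that section 5 may not be the complete schedule. It does not say that these are the only occasions, and it leaves collection to the Clinical Assessment Core. Section 4, the floor of five observations per measure in the power paragraph, and the 18-month time point in RQ2b all point to more than three. Appendix 1 or the Core protocol may list the 18- and 30-month visits. This stands, and it makes the power point conditional. It does not remove the conflict between sections 4 and 5.

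Secondly, the power paragraph is about growth curve models, and its minimum can be read as the smaller of .86 and .91. The Data Analytic Strategy also allows residualized change or outcome-only analysis for some variables. This narrows the claim. But it assigns those alternatives to no named measure, and RQ1a and RQ1b put all three measures in trajectory comparisons. Both figures for 80 children assume at least five assessments.

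Thirdly, the loss may be small. For a slope test with large true slope variation between children, three visits cost almost nothing. That is correct, and it is why the result is given as a range.

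**Conclusion.** The schedule conflict is certain from the text and needs no statistical assumption. The power consequence is conditional: if section 5 governs, .86 is not a minimum for the ADOS, Mullen or Vineland. If section 4 governs, it can stand on visit count.

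At N=80, with 1:1 allocation and two-sided .05, three visits give about .78 to just under .86 for a slope test calibrated to the plan's own figure, and about .72 to .73 for the endpoint contrast. The CSBS on the section 5 ages stays at about .85 or slightly above for a slope test, but falls to about .74 to .75 for the endpoint contrast. These are illustrations and do not bound the shortfall.

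A reader might infer three stronger things that the documents do not support:

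- That .90 and .86 are arithmetic errors. They agree with each other, and nothing shows them to be wrong for five visits.
- That the 18-month outcomes will certainly be missed. The unseen timeline and Core protocol may provide for them.
- That the slope range caps the loss, or that the CSBS is safe. Both hold only if the slope is what is tested, and the plan also intends group contrasts at points along the curve.

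This should be fixed. Confidence is high on the textual conflict and low on the exact size of the power loss.

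**What to change.** Give one assessment schedule per measure, and make section 4 (including RQ2b), section 5, Appendix 1 and the Clinical Assessment Core protocol agree with it.

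- **If the section 5 schedule governs:** rerun and restate power for the three-visit measures, giving the estimand, the scale of d, the slope and residual variances and the sidedness used. Limit the .86 minimum to growth models on outcomes that have the five-visit schedule assumed in the calculation. The CSBS has five visits at other ages, so it needs its own line. Correct the 18-month time point in RQ2b.
- **If the section 4 schedule governs:** list the 18- and 30-month assessments in section 5, and say whether the 15- and 21-month CSBS assessments remain. The .86 can then stand on visit count.

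The first route costs wording and a rerun of the power program, with no added visits or children and a less favourable stated power for the three measures. The second adds two listed assessments per child (18 and 30 months) to section 5; this is extra work only if the Core does not already carry them out.

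### The stated minimum power of .86 covers growth-curve comparisons only; an outcome-only comparison, which the plan also permits, has about .60 with 80 children

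*Combined protocol and SAP*

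**What the plan says.** Section 6, Data Analytic Strategy, names three forms of comparison between the arms: "The research aims compare growth trajectories (or residualized change, or outcome only, depending on the dependent variable of interest"). It does not say which dependent variable gets which form.

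Section 6, Power Analyses, deals with the first form: "Power for growth curve modeling was estimated using a power estimation program developed for HLM models". The inputs are given as "we set alpha at .05 and we anticipated as few as 5 and as many as 25 observations per child (per measure"), with an ICC of .10. The results for five assessments and linear change are "92 subjects would give us a power=.90 to detect an effect of d=.50 (which corresponds to a medium effect) with five time points" and "If attrition drops the sample size to 80 subjects, we will still have power equal to .86 to detect a medium-sized effect". For quadratic change with 15 or more assessments the figures are .95 and .91. The paragraph then concludes: "Thus, the minimum power to detect medium effects with 80 subjects is .86".

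Section 5, Dependent Variables, has these measures "coded by raters blind to treatment condition before treatment at 12 months and again at 24 months and 36 months of age", so a pre-treatment value exists for them. Section 5, Random Assignment, adjusts for pretest variables that correlate with outcome, but only if the groups turn out not to be equivalent on them.

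**The concern.** The concluding sentence speaks of medium effects in general, while the calculation behind it covers one of three permitted forms of analysis. An outcome-only comparison uses one value per child. Neither the number of assessments nor the ICC enters it, so the growth-curve figure cannot carry over, whether or not it is right for growth curves.

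If an outcome is analysed this way with 80 children, the chance of missing a medium effect is about 40% (1 − .60), not the 14% (1 − .86) that the sentence implies. A null result could then be read as evidence against a medium benefit that the analysis had little chance of detecting. An outcome-only analysis would also leave unused the 12-month value that the plan already collects.

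**Working it through.** **Inputs from the documents (Section 6, Power Analyses).** Alpha .05; d=.50; N=92, or 80 after attrition; stated power .90 and .86.

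**Assumptions where the documents are silent.** The test is two-sided (one-sided also shown). Allocation is 1:1. d is a standardized mean difference at one time point. The baseline-outcome correlation r is not given, so a range is used.

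**1. The plan's own figure.** The .90 and .86 cannot be rebuilt from the stated inputs, because the slope variance and the scale of d in the growth routine are missing. Two-sided five-visit slope tests under various scalings gave about .08 to .52 at N=92, and a comparison of five-visit means gave .99. The two stated values do agree with each other. Power .90 needs a noncentrality of 1.960 + 1.282 = 3.242. At N=80 this becomes 3.242 × √(80/92) = 3.023, and Φ(3.023 − 1.960) = .856.

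**2. Outcome only.** This is a two-sample t test with noncentrality d × √(N/4) and N − 2 degrees of freedom.

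| N | Noncentrality | Power, two-sided | Power, one-sided |
|---|---|---|---|
| 92 | .50 × √23 = 2.398 | .660 | .769 |
| 80 | .50 × √20 = 2.236 | .598 | .716 |

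At N=80 the two-sided value is 26 points below .86. Solving for the effect that gives .86 with 80 children yields d of about .69. Solving for the sample that gives .86 at d=.50 yields about 150 children.

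**3. Residualized change.** Adjusting for baseline shrinks the residual SD by √(1 − r²), so the effect becomes .50/√(1 − r²), with N − 3 degrees of freedom (two-sided).

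| r (assumed) | .50/√(1 − r²) | Power, N=92 | Power, N=80 |
|---|---|---|---|
| 0 | .500 | .66 | .60 |
| .3 | .524 | .70 | .64 |
| .5 | .577 | .78 | .72 |
| .6 | .625 | .84 | .79 |
| .7 | .700 | .91 | .87 |

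Power of .86 at N=80 is reached when r is about .69.

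**The case against.** The strongest reply is that the power paragraph opens by saying it concerns growth curve modeling, lists four figures, and then names the lowest. On that reading the final sentence has an implied scope and nothing is miscalculated. This is fair as to the arithmetic. It does not cure the sentence, because the same section permits two other forms and gives no power for either.

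Second, mixed models are the main strategy, and the Aim 1 questions in Section 4 are framed as trajectories. Outcome only appears once, in a parenthesis, tied to no variable. That stands as a limit: a reader might infer that a particular main outcome is underpowered, and the documents do not support this because they assign no outcome to that form.

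Third, a reader might infer that residualized change also has .66/.60, by taking the ICC of .10 as the correlation between baseline and follow-up. The documents do not support that. The ICC equals that correlation only in a random-intercept model. The plan specifies growth curves and gives no slope variance or intercept-slope covariance, so the ICC does not fix a 12-to-24- or 12-to-36-month correlation. The value .66/.60 is the floor at r=0.

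Fourth, the scale of d in the growth routine is unknown, so the 26-point gap may not compare like with like. This stands as a caveat. The scale used here does match the Data Analytic Strategy, which defines effect size as a mean difference over the control or pooled SD.

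Fifth, some baseline adjustment is planned. It depends on observed imbalance, so it does not secure the gain in precision in advance.

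**Conclusion.** The concern holds as a point of scope. The .86 is a minimum over growth-curve comparisons, not over the analyses that the plan permits. For outcome-only comparisons, power at d=.50 is about .66 with 92 children and .60 with 80, and one-sided testing does not bring it to .86. For residualized change no single figure can be stated: .86 with 80 children is met only if r is about .69 or more, and the plan gives no r.

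These figures rest on two-sided testing (except where marked), 1:1 allocation, and d as a single-time-point standardized difference. A reader might also infer that the growth-curve .90 and .86 are wrong. Failure to rebuild them does not show that, since needed inputs are not stated, and this point does not depend on it.

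**What to change.** **Power Analyses.** Limit the closing sentence to growth-curve comparisons and add, for example: *For outcome-only comparisons, power to detect d=.50 (two-sided .05, equal arms) is about .66 with 92 children and .60 with 80. For residualized change it depends on the baseline-outcome correlation r, which is assumed: .66/.60 at r=0, .70/.64 at r=.3, .78/.72 at r=.5, .91/.87 at r=.7.* If a detectable effect is wanted for outcome only, it is d of about .69 at .86 power with 80 children.

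**Data Analytic Strategy.** For dependent variables collected at 12 months, replace outcome only by an analysis that uses the 12-month value: the longitudinal mixed model, or the 12-month value as a prespecified covariate whether or not the arms look balanced. Expressive Language Phase has four ordered categories, so it needs an ordinal model rather than a linear one.

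**Cost.** The first change is wording. The second is a modest change of analysis for any variable that would have been tested on outcome alone. Neither needs more children, visits or measures. The downside is a less favourable stated power for some analyses.
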